8.3.1.3. Discontinuation from the Study

The criteria for enrollment must be followed explicitly. If a patient who does not meet enrollment criteria is inadvertently enrolled, the investigator should contact Lilly or its designee to discuss whether the patient should be discontinued from study drug. If the patient is discontinued from study drug, the patient should remain in the study to provide the follow-up data needed for the primary analysis (Week 12) of the entire intention-to-treat (ITT) population.

Patients may choose to withdraw from the study for any reason at any time, and the reason for early withdrawal will be documented.

In addition, patients will be discontinued from the study in the following circumstances:

- Patient enrolls in any other clinical trial involving an investigational product or enrollment in any other type of medical research judged not to be scientifically or medically compatible with this study.
- Investigator decides that the patient should be withdrawn. If this decision is made because of an intolerable AE or a clinically significant laboratory value, the study drug is to be discontinued and appropriate measures are to be taken. Lilly (or designee) is to be notified immediately.

- Lilly (or designee) decides that the patient should be withdrawn.
- Patient is noncompliant with protocol procedures.
- Patient withdraws consent.
- Investigator or Lilly (or designee), for any reason, stops the study.

Patients who discontinue the study early will have Early Termination procedures and follow-up performed as shown in the study schedule ([Attachment 1](#)).

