Unless otherwise specified, the efficacy and safety analyses will be conducted on a modified intent-to-treat basis (mITT) (Gillings and Koch 1991). This analysis set includes all data from all randomized patients who received at least 1 dose of study drug. In addition, the primary and secondary efficacy analyses for the double-blind period will be repeated in a subset of mITT analysis set, the per protocol (PP) set, which is defined as all randomized patients who are compliant with treatment, who do not have significant protocol violations, and whose investigator site does not have significant GCP issues that require a report to the regulatory

agencies. Analysis of structural progression (van der Heijde mTSS) will be conducted on the mITT population using patients with available baseline and at least 1 postbaseline value.

Sensitivity analyses of the primary endpoints may be conducted and will be described in the SAP.

Missing Data Imputation:

In accordance with precedent set with other Phase 3 RA trials (Keystone et al. 2004, 2008, 2009; Cohen et al. 2006; Smolen et al. 2008, 2009), the following methods for imputation of missing data will be used:

1. Nonresponder imputation (NRI): All patients who discontinue the study or the study treatment at any time for any reason will be defined as nonresponders for the NRI analysis for categorical variables, such as ACR20/50/70, from the time of discontinuation and onward. Patients who receive rescue therapy at Week 16 will be analyzed as nonresponders after Week 16 and onward. Randomized patients without available data at a postbaseline visit will be defined as nonresponders for the NRI analysis at that visit.

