6.1. General Considerations

This plan describes *a priori* statistical analyses for efficacy, health outcomes, and safety that will be performed.

Statistical analysis of this study will be the responsibility of Lilly.

For continuous measures, summary statistics will include the sample size, means, standard deviations (SDs), medians, minimums, 1st quartiles (Q1), 3rd quartiles (Q3), and maximums.

For categorical measures, summary statistics will include the sample size, frequency counts, and percentages.

All statistical tests of treatment effects will be performed at 2-sided significance levels of 0.05, unless otherwise stated.

All p-values will be rounded up to 3 decimal places. For example, any p-value strictly greater than 0.049 and less than or equal to 0.05 will be displayed as 0.050. This guarantees that on any printed statistical output, the unrounded p-value will always be less than or equal to the displayed p-value. A displayed p-value of 0.001 will always be understood to mean ≤ 0.001 . Likewise, any p-value displayed as 1.000 will be understood to mean > 0.999 and ≤ 1 .

Lilly will use both an effectiveness estimand (that is, the relative effect attributable to the originally randomized treatments, baricitinib and placebo, at the primary time point in all treated patients, even if patients change treatment) and an efficacy estimand (that is, the relative effect attributable to the originally randomized treatments, baricitinib and placebo, at the primary time point in all treated patients if taken as directed) to evaluate efficacy measures at the primary time point of Week 12 for Study JAGS. All primary and secondary endpoints related to improvements in symptomatic features (that is, RA signs and symptoms, physical function, and patient-reported outcomes) are assessed prior to patients having the option to receive rescue therapy. Therefore, the only practical difference between the efficacy and effectiveness estimands for these endpoints concerns assumptions about patient response after permanent discontinuation of study drug or from the study prior to the analysis time point.

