6.3. Handling of Dropouts or Missing Data

6.3.1. *Missing Data Imputation for Efficacy and Health Outcomes Endpoints*

In accordance with precedent set with other Phase 3 RA trials (Keystone et al. 2004, 2008, 2009; Cohen et al. 2006; Smolen et al. 2008, 2009), the following methods for imputation of missing data will be used when appropriate:

1. Non-responder imputation

All patients who discontinue the study or permanently discontinue the study treatment at any time for any reason will be defined as nonresponders for the NRI analysis for categorical variables, such as ACR20/ACR50/ACR70, from the time of discontinuation and onward. If, at the time of study database lock, there are patients with unresolved interruptions of study drug (ie, not yet re-started, to be confirmed as a temporary interruption, and not yet permanently discontinued), these patients will be treated as having been permanently discontinued from study drug for the purposes of data imputation for analysis purposes. Patients who are randomized to baricitinib 4 mg and who receive rescue therapy starting from Week 16 will be analyzed as nonresponders after the rescue visit and onward. Patients who are randomized to placebo and who receive rescue therapy starting from Week 16 will be analyzed as nonresponders after the rescue visit and on or prior to Week 24. Randomized patients without available data at a postbaseline visit will be defined as nonresponders for the NRI analysis at that visit.

2. Modified baseline observation carried forward

The mBOCF method will be used for the analysis of secondary continuous endpoints (unless otherwise stated). For patients who discontinue the study or permanently discontinue the study treatment because of an AE, including death and abnormal lab results reported as AEs, the baseline observation will be carried forward to subsequent time points for evaluation. For patients who discontinue the study or permanently discontinue the study treatment for reason(s) other than an AE, the last nonmissing postbaseline observation prior to discontinuation will be carried forward to the subsequent time points for evaluation. If, at the time of study database lock, there are patients with unresolved interruptions of study drug (ie, not yet re-started, to be

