6.11.1. Primary Outcome and Methodology

The primary efficacy measure will be the proportion of patients achieving ACR20 at Week 12 based on the change in ACR response values from baseline. ACR20 is defined as at least 20% improvement from baseline in the following ACR Core Set variables:

- TJC68
- SJC66
- An improvement of $\geq 20\%$ from baseline in at least 3 of the following 5 assessments:
 - Patient's assessment of pain (VAS)
 - Patient's Global Assessment of Disease Activity (VAS)
 - Physician's Global Assessment of Disease Activity (VAS)
 - Patient's assessment of physical function as measured by the HAQ-DI
 - Acute phase reactant as measured by hsCRP

Refer to the algorithm to calculate ACR response in [Appendix 1](#).

The primary efficacy analysis compares ACR20 at Week 12 between baricitinib and placebo using the mITT population. The PP population results will be used as supportive to the mITT results. A logistic regression model with treatment, country/region, and joint erosion status (1-2 joint erosions plus seropositivity versus at least 3 joint erosions) in the model will be used to test the treatment difference between baricitinib and placebo in the proportion of patients achieving ACR20 response at Week 12 using the Wald test at 2-sided significance level of 0.05. The NRI approach will be used to impute response status for patients with completely missing data. The p-value and 95% CI of odds ratio from the logistic regression model will be reported. The 95%

CI of responder rate difference will be calculated using the Newcombe-Wilson method (Newcombe 1998) without continuity correction. Treatment-by-country/region interaction will be added to the logistic regression model as a sensitivity analysis and results from this model will be compared to the primary model. If the treatment-by-country/region interaction is significant at a 2-sided 0.1-alpha level, the nature of this interaction will be inspected as to whether it is quantitative (ie, the treatment effect is consistent in direction but not size of effect) or qualitative (the treatment is beneficial in some but not all countries). If the treatment-by-country/region interaction effect is found to be quantitative, results from the primary model will be presented. If the treatment-by-country/region interaction effect is found to be qualitative, further inspection will be used to identify in which countries baricitinib is found to be more beneficial.

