Further, for some AEs of interest, duration of the TEAE may be summarized or listed within patient AE listings. The duration of each event will be defined as the end date of AE minus the start date of treatment-emergence of the AE plus 1 day. If an AE has not ended by the date of study drug discontinuation, early discontinuation of the study/period, or completion of the study, it will be censored as of that appropriate final date.

In general, summaries of TEAEs, SAEs, AEs that lead to discontinuation from the study, and AEs that lead to temporary interruption or permanent discontinuation of study drug will include the number of patients in the safety population (N), frequency of patients experiencing the event (n), and percent of patients experiencing the event ($n/N \times 100$), and the exposure-adjusted incidence rate (EAIR). The EAIR will be expressed as the number of patients experiencing an

AE (n) per 100 patient years of exposure to treatment and is derived as 100 times the number of patients with the event divided by the sum of all patient exposure times (in years) to the treatment for the study/period. For any events that are gender-specific based on the displayed PT, the denominator used to compute the percentage will only include patients from the given gender. Treatment comparisons between treatment groups will be made using the Fisher exact test.

In an overview table, the number and percentage of patients in the safety population who experienced a death, a serious adverse event (SAE) (International Conference on Harmonisation [ICH]-defined, protocol-defined, and ICH- or protocol-defined), discontinuation from the study due to an AE or death, permanent discontinuation from study drug due to an AE or death, temporary interruption from study drug due to an AE, temporary interruption of study drug due to a lab abnormality, a TEAE, a TEAE rated as severe, or an AE possibly related to study drug based on the opinion of the investigator will be summarized by treatment.

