 - a. If at least three items are $\geq\chi\%$, then STOP – assign the patient as a responder for ACR χ .
 - b. If at least three items are $<\chi\%$, then STOP – assign the patient as a nonresponder for ACR χ .
 - c. If less than three items are $\geq\chi\%$, then STOP – assign ACR χ response as blank.

To calculate the ACRx response at post baseline visits up to Week 52 using NRI:

- Step 1: Calculate the % improvement at the visit for all seven parameters as described above.
- Step 2: If all seven parameters are missing at the visit, or if the patient discontinued from the study prior to reaching the visit, then STOP – assign the patient as a nonresponder for ACRx.
- Step 3: If at least one of the seven parameters is non-missing at the visit and the patient is still enrolled in the study, then use LOCF to fill in any missing values.
- Step 4: If TJC68 AND SJC66 are BOTH $\geq\chi\%$, then proceed to step 5. If both are nonmissing but one or both is $<\chi\%$, then STOP – assign the patient as a nonresponder for ACR χ . If either or both are missing, then STOP – assign the patient as a non-responder for ACR χ .
- Step 5: Consider the following five variables: PATPAIN, PATGA, PHYGA, HAQ, hsCRP.
 - o If three or more of the five items are non-missing, then:
 - If three or more of the five items are $\geq\chi\%$, then STOP – assign the patient as a responder for ACRx.
 - If less than three of those five items are $\geq\chi\%$, then STOP – assign the patient as a non-responder for ACRx.
 - o If three or more of the five items are missing, then STOP – assign the patient as a non-responder for ACRx.

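### The Appendix 1 NRI algorithm for ACR20 omits permanent study-drug discontinuation, which SAP 6.3.1 and Protocol 12.2.1 both score as nonresponse

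*SAP*

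**What the plan says.** **General rule.** SAP 6.3.1 (item 1, NRI) states: "All patients who discontinue the study or permanently discontinue the study treatment at any time for any reason will be defined as nonresponders". The rule runs from the time of discontinuation and names ACR20, ACR50 and ACR70. Protocol 12.2.1 has the same rule: "All patients who discontinue the study or the study treatment at any time for any reason will be defined as nonresponders". Only the SAP adds that the treatment stop must be permanent.

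**Primary analysis.** SAP 6.11.1 refers the reader to Appendix 1 for calculating ACR response. On missing data it says: "The NRI approach will be used to impute response status for patients with completely missing data". It does not cite 6.3.1.

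**Algorithm.** In the NRI part of Appendix 1, Step 2 assigns nonresponse "If all seven parameters are missing at the visit, or if the patient discontinued from the study prior to reaching the visit". Step 3 begins "If at least one of the seven parameters is non-missing at the visit and the patient is still enrolled in the study" and fills the missing components by LOCF. Steps 4 and 5 then score the components. Appendix 1 describes itself as a basis for dataset programming, and it does not refer back to 6.3.1.

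**The concern.** Leaving the study and stopping study drug are different events in these documents. SAP 6.1 says the estimand question at Week 12 "concerns assumptions about patient response after permanent discontinuation of study drug or from the study prior to the analysis time point". SAP 6.14.1 tabulates the two separately: "discontinuation from the study due to an AE or death, permanent discontinuation from study drug due to an AE or death". Protocol 8.3.1.3 keeps one off-drug group under observation: "If the patient is discontinued from study drug, the patient should remain in the study to provide the follow-up data needed". That passage concerns Week 12 data from patients enrolled in error and then taken off drug.

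The general rule covers both events, while the algorithm covers only leaving the study. Two competent programmers could derive different Week 12 ACR20 values from the same data, and the one who follows Appendix 1 and 6.11.1 to the letter departs from the protocol. At stake are the reported ACR20 rates, their difference and the odds ratio. ACR50 and ACR70 use the same algorithm.

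**Working it through.** **1. Trace one patient through both rules.** Take a patient who permanently stops study drug at Week 8, stays in the study, attends Week 12 and has at least one ACR component recorded there.

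| Step | SAP 6.3.1 / Protocol 12.2.1 | SAP Appendix 1 (NRI) |
|---|---|---|
| Off study drug | Nonresponder from Week 8 on | Not a condition at any step |
| Left the study or all seven components missing? | Not needed | No, so Step 2 does not apply |
| Still enrolled with one or more components? | Not needed | Yes, so Step 3 fills gaps by LOCF |
| Component scoring | Not reached | Steps 4 and 5: responder if the 20% criteria are met |
| Week 12 ACR20 | Nonresponder | Can be a responder |

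Because of the LOCF in Step 3, such a response could rest partly on values recorded while the patient was still on drug.

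**2. Compare a neighbouring rule.** The NRI rule for the DAS28 binary endpoints in SAP Appendix 2 names discontinuation of treatment as well as of the study. The clause is present there and absent for ACR, which points to an oversight.

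**3. Reproduce the planned power.** Inputs from SAP 5.2 and Protocol 12.1: 144 per arm, 60% versus 35%, two-sided chi-square test at 0.05.

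- Mean rate = (0.60 + 0.35)/2 = 0.475
- SE under the null = √(2 × 0.475 × 0.525/144) = 0.05885
- SE under the alternative = √(0.60 × 0.40/144 + 0.35 × 0.65/144) = 0.05698
- Power = Φ[(0.25 − 1.960 × 0.05885)/0.05698] = 0.991, agreeing with the stated 99%
- Odds ratio = (0.60/0.40)/(0.35/0.65) = 2.79

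**4. Size of the discrepancy.** One reclassified patient moves an arm by 1/144 = 0.69 points. The number of off-drug, in-study responders at Week 12 is not in the documents. *Assumption for illustration:* 60% and 35% are the rates under 6.3.1, and Appendix 1 adds k responders, so an arm's rate becomes p + k/144. Power uses the step 3 formula.

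| Extra responders under Appendix 1 | Baricitinib % | Placebo % | Difference (points) | Odds ratio | Power |
|---|---|---|---|---|---|
| None | 60.0 | 35.0 | 25.0 | 2.79 | 99.1% |
| 1, baricitinib only | 60.7 | 35.0 | 25.7 | 2.87 | 99.4% |
| 3, baricitinib only | 62.1 | 35.0 | 27.1 | 3.04 | 99.7% |
| 6, baricitinib only | 64.2 | 35.0 | 29.2 | 3.33 | 99.9% |
| 1, placebo only | 60.0 | 35.7 | 24.3 | 2.70 | 98.7% |
| 3, placebo only | 60.0 | 37.1 | 22.9 | 2.54 | 97.6% |
| 6, placebo only | 60.0 | 39.2 | 20.8 | 2.33 | 94.6% |
| 1, 3 or 6 in each arm | up to 64.2 | up to 39.2 | 25.0 | 2.78 | 99.1% |

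A much more extreme assumption is needed to threaten the test. With 10% of the placebo arm affected, all of them responders and none on baricitinib, the comparison is 60% versus 45% and power is 72.4%.

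**The case against.** The strongest reply is that 6.3.1 already governs. It names the ACR endpoints, SAP Table 6-1 assigns them to NRI, and the Appendix 1 block uses that defined term in its heading. On this reading the appendix is component-scoring logic, not a full list of nonresponse triggers. It also omits the post-rescue rule of 6.3.1, although it covers visits to Week 52. Further, the sentence in 6.11.1 does not say that NRI applies *only* to patients with no data; it may simply contrast them with patients who have partial data and get LOCF. Finally, the affected group may be tiny: the only passage that keeps off-drug patients in the study for Week 12 data concerns those enrolled in error.

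Parts of this stand. The sponsor's intention is probably the 6.3.1 rule, 6.11.1 is loose rather than restrictive, the count is unknown, and the range of 1 to 6 has no source. The rescue omission cannot affect Week 12, because rescue starts at Week 16.

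The conflict remains, however. Appendix 1 is written for programming, ends in a responder status and never defers to 6.3.1. The primary analysis points to it without citing 6.3.1, whereas the secondary SDAI analysis in 6.11.2 does cite that section. Protocol 12.2.1 also requires changes to its analysis methods to be described and justified, and the SAP gives no reason for dropping the treatment clause.

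**Conclusion.** The concern holds and should be fixed. As written, Appendix 1 can score as a responder a patient whom the SAP body and the protocol both define as a nonresponder on the primary endpoint. The certain part of the size is 0.69 percentage points per affected patient per arm; the number of patients and the direction of any shift are unknown. Under the illustrative 1 to 6 responders in a single arm, the difference lies between 20.8 and 29.2 points and the odds ratio between 2.33 and 3.33, against 25.0 points and 2.79. Equal numbers in both arms leave the difference unchanged. The primary test is unlikely to turn on this. What needs repair is that the primary endpoint does not have a single derivation.

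**What to change.** Before unblinding:

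1. In Appendix 1 (NRI), Step 2, add permanent discontinuation of study treatment before the visit, per Section 6.3.1, as a third route to nonresponse.
2. In Step 3, require that the patient is still enrolled and has not permanently discontinued study treatment. This is redundant once Step 2 is amended, but it makes the logic explicit.
3. In 6.11.1, replace the description of who receives NRI with a reference to Section 6.3.1, as 6.11.2 already does for SDAI.

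For rescue at later visits, point Appendix 1 to the existing 6.3.1 rule and add no new condition. The same pointer would cover the 6.3.1 rule for drug interruptions still unresolved at database lock.

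The cost is three wording edits and one programming condition, with no new data. Relative to Appendix 1 as written, ACR rates can only stay the same or fall slightly.

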Appendix 2. Details of Efficacy and Health Outcomes Measures

van der Heijde Modified Total Sharp Score

X-rays of the hands/wrists and feet will be scored (according to the Bioclinica predefined imaging charter) for structural progression as measured using the mTSS (van der Heijde, 2000). This methodology quantifies the extent of bone erosions for 44 joints and joint space narrowing for 42 joints with higher scores representing greater damage.

Structural progression will be measured using the mTSS. During screening, all patients meeting entry criteria will have a single posteroanterior radiographic assessment of the left and right hand/wrist and a single dorsoplantar radiographic image taken of the left and right foot. Alternatively, images taken within 4 weeks prior to baseline may be used. Images taken at screening (or within 4 weeks of screening) will be reviewed centrally by qualified readers for evidence of erosive bony change(s). These initial radiographs will serve as the baseline radiographs for comparison throughout the study.

Additional radiographs (ie, a single posteroanterior view of each hand and a single dorsoplantar view of each foot) will be obtained at Week 16, Week 24 (the primary evaluation), and Week 52 (for the purposes of demonstrating durability of structural preservation), as shown in the study schedule (See Protocol Appendix). For patients who discontinue prematurely from the study, x-rays will be performed at the early termination visit only if the previous x-rays were taken more than 12 weeks earlier.

Bone Joint Erosion Score

The joint erosion score is a summary of erosion severity in 32 joints of the hands and 12 joints of the feet. The maximum erosion score for a hand joint is 5 and for a foot joint is 10. Thus, the maximal erosion score is 280 for a time point (160 for both hands/wrists and 120 for both feet). Each joint is scored according to the surface area involved from 0 to 5 for hand joints and 0 to 10 for the foot joints. The highest score (5 for the hand and 10 for the foot) indicates extensive loss of bone from more than one half of the articulating bone. A score of 0 in either the hand or foot joints indicates no erosion.

Erosion for each hand joint (16 joints per hand) is graded on the following scale.

- 0 - Normal (no erosion)
- 1 - Discrete small erosion
- 2 - Two discrete erosions or one large erosion not passing the joint middle line
- 3 - One large erosion passing the joint middle line of the bone or combination of the above
- 4 - Combinations of discrete and/or large erosions adding up to 4
- 5 - Combinations of discrete and/or large erosions adding up to 5 or more
- NA - Not assessable due to poor radiographic depiction

S - Surgically modified (e.g. joint replacement, amputation, or other surgery)

Discrete erosions will be graded 1 if small and 2 or 3 if larger, with a score of 3 if the erosion is large and extends across the imaginary middle of the bone. Discrete erosions of each grade will then be summed over both sides of the joint to a maximum of 5 to give a total score for each location in the hands. When erosions in the carpal bones of the wrist are confluent rather than discrete and focal, the percent surface eroded will be scored from 0 to 5 in approximately 20% intervals. A score of 'NA' will be assigned in the case that the location is not evaluable due to advanced subluxation or poor radiographic depiction. A score of 'S' will be assigned in the case of joint replacement, amputation, or other surgery.

Erosion for each side of a foot joint (6 joints per foot) is graded on the following scale.

0 - Normal (no erosion)

1 - Discrete small erosion

2 - Two discrete erosions or one large erosion not passing the joint middle line

3 - One large erosion passing the joint middle line

4-10 - Combination of the above conditions.

NA - Not assessable due to poor radiographic depiction

S - Surgically modified (e.g. joint replacement, amputation, or other surgery)

Since both sides of each foot joint are graded, the maximum score for a foot joint is 10 (a score of 5 on each side).

Joint Space Narrowing (JSN) Score

The JSN score summarizes the severity of JSN in 30 joints of both hands and 12 joints of both feet. Assessment of JSN for each hand (15 joints per hand) and foot (6 joints per foot), including subluxation, is scored from 0 to 4, with 0 indicating no (normal) JSN and 4 indicating complete loss of joint space, bony ankylosis, or luxation. Thus, the maximum JSN score is 168 (120 for both hands/wrists and 48 for both feet) at a time point. JSN for each hand and foot joint is graded on the following scale:

0 - Normal or no narrowing

1 - Asymmetrical and/or minimal narrowing- up to 25%

2 - Definite narrowing with loss of up to 50% of the normal space

3 - Definite narrowing with loss of 50-99% of the normal space or subluxation

4 - Absence of a joint space, presumptive evidence of ankylosis, or complete luxation

NA - Not assessable due to poor radiographic depiction

S - Surgically modified (e.g. joint replacement, amputation, or other surgery)

Total Modified Sharp Score (mTSS)

The total mTSS score at a time point is the sum of the erosion (maximum of 280) and JSN (maximum of 168) scores, for a maximum score of 448.

Handling of Missing Joint Data

Refer to a separate document for a detailed description of imputation of missing joint data.

Adjudication Process

The read of x-ray images will be performed by 2 independent readers. An adjudication of results will be in place to show any discrepancy between the 2 independent readers. The adjudication process will involve re-reading by a third independent reader. Cases that require adjudication will be identified once the 2 primary independent reviews are completed. To ensure a consistent read by the 2 independent readers, an inter-/intra-reader variability assessment will be evaluated. Refer to the Bioclinica imaging charter and a separate document describing missing data imputation for more details.

ACR Core Set

The individual components that make up the ACR Core Set of measures for RA are:

Tender Joint Count (TJC)

For ACR measures, the number of tender and painful joints will be determined by examination of 68 joints (34 joints on each side of the patient's body). These 68 joints will be assessed and classified as tender, not tender, or not evaluable. The number of tender joints ranges from 0 to 68. The algorithm to calculate TJC is in the Joint Assessment section of this Appendix.

Swollen Joint Count (SJC)

For ACR measures, the number of swollen joints will be determined by examination of 66 joints (33 joints on each side of the patient's body). These 66 joints will be assessed and classified as swollen, not swollen, or not evaluable. The number of swollen joints ranges from 0 to 66. Refer to the Joint Assessment section of this Appendix for the algorithm to calculate SJC.

Patient's Assessment of Pain (VAS)

The patient will be asked to assess his or her current level of pain by marking a vertical tick on a 100-mm horizontal VAS with the left end marked as "no pain" and the right end marked as "worst possible pain". Results will be expressed in millimeters measured between the left end of the scale and the crossing point of the vertical line of the tick. This procedure is applicable for all VAS scales used in the trial.

Patient's Global Assessment of Disease Activity (VAS)

The patients will be asked to give an overall assessment of how their rheumatoid arthritis is affecting them at present by marking a vertical tick on a VAS from "very well" to "very poor".

Physician's Global Assessment of Disease Activity (VAS)

The physician's assessment of a patient's disease activity assessed at the visit will be recorded using the VAS from "none" to "extremely active arthritis".

Patient's Assessment of Physical Function (HAQ-DI)

The patient will be asked to complete the HAQ-DI to measure the impact of arthritis on their ability to function in daily life. The HAQ-DI functional disability index score ranges from 0 to 3, with lower scores indicating better physical functioning. See Section HAQ-DI of this Appendix for the algorithm to calculate the HAQ-DI functional disability index score.

High sensitivity C-Reactive Protein (hsCRP)

hsCRP will be the ACR Core Set measure of acute phase reactant. It will be measured at the central laboratory.

Joint Assessment

Each of 28 or 68 joints will be evaluated for tenderness and 28 or 66 joints will be evaluated for swelling (hips are excluded for swelling) at the specified visits as shown in the schedule of events of the protocol. The 68/66 joint count will be performed at screening, Week 0 (baseline), Week 1 to Week 24 in Part A, Week 24 to Week 52 in Part B, end of treatment, and at the follow-up visit. For scores using 28 joints, the following subset will be assessed (both right and left side):

- Shoulder,
- Elbow,
- Wrist,
- Metacarpophalangeal (MCP) I, II, III, IV, and V,
- Thumb interphalangeal,
- Proximal interphalangeal (PIP) II, III, IV, and V,
- KJannee.

Joints will be assessed for tenderness by pressure and joint manipulation on physical examination. Any positive response on pressure, movement, or both will then be translated into a single tender-versus non-tender dichotomy. Joints will be classified as either swollen or not swollen. Swelling is defined as palpable fluctuating synovitis of the joint. Swelling secondary to osteoarthritis will be assessed as not swollen, unless there is unmistakable fluctuation.

The following joint count imputation rules will be applied.

(1). Joints that had any of the following procedures or disease conditions that occur at the screening (Visit 1) up to and including baseline (Visit 2) will be imputed as follows:

- **Arthroplasty, fusion, synovectomy, ankylosis, amputation, injury, fracture, and infection:** these will be considered “non-evaluable” from baseline up to end of the study. Joints that include “non-evaluable” joints will be prorated from baseline up to end of the study. For example, the swollen joint count score for 6 swollen plus 2 “non-evaluable” joints for DAS28 is calculated as $[6/(28-2)]*28 = 6.46$.
- **Injection:** joints that have received intra-articular and bursal injections will be collected in the data but set to painful/tender or swollen after the injection for 6 months (up to Week 24 [Visit 11]).

(2). Joints that had any of the following procedures or disease conditions that occur postbaseline (anytime during treatment with the study drugs) will be imputed as follows:

- **Amputation:** amputation that occurs postbaseline will be considered “non-evaluable” from the visit after amputation up to end of the study. Joints that include “non-evaluable” joints will be prorated from the visit after amputation up to end of the study. For example, the swollen joint count score for 6 swollen plus 2 “non-evaluable” joints for DAS28 is calculated as $[6/(28-2)]*28 = 6.46$.

- **Arthroplasty, fusion, synovectomy, and ankylosis:** if any of these procedures occur postbaseline, joints will be set to painful/tender or swollen from the visit after the procedure up to end of the study.
- **Infection, injury, and fracture:** if any of these conditions occur postbaseline, joints will be set to painful/tender or swollen from the visit after the condition until the condition is resolved.
- **Injection:** joints that have received intra-articular and bursal injections postbaseline will be collected in the data but set to painful/tender or swollen after the injection for 6 months or end of study (whichever comes first).

The number of tender and swollen joints will be calculated by summing all joints. For patients who have an incomplete set of joints evaluated, the joint count will be adjusted to a 28- or 68-joint count for tenderness and a 28- or 66-joint count for swelling by dividing the number of affected joints by the number of evaluated joints and multiplying by 28 or 68 for tenderness and 28 or 66 for swelling.

Disease Activity Score-Erythrocyte Sedimentation Rate (DAS28-ESR) and Disease Activity Score-High Sensitivity C-Reactive Protein (DAS28-hsCRP)

The DAS28 is a measure of disease activity in 28 joints that consists of a composite numeric score of the following variables: TJC, SJC, hsCRP or ESR, and Patient's Global Assessment of Disease Activity (Vander Cruyssen et al. 2005). The 28 joints to be examined and assessed as tender or not tender for TJC and as swollen or not swollen for SJC include 14 joints on each side of the patient's body: the 2 shoulders, the 2 elbows, the 2 wrists, the 10 metacarpophalangeal joints, the 2 interphalangeal joints of the thumb, the 8 proximal interphalangeal joints, and the 2 knees (Smolen et al. 1995). The following equation will be used to calculate the DAS28- hsCRP (Vander Cruyssen et al. 2005):

$$\text{DAS28-hsCRP} = 0.56(\text{TJC28})^{1/2} + 0.28(\text{SJC28})^{1/2} + 0.36(\ln(\text{hsCRP} + 1)) + 0.014(\text{VAS}) + 0.96$$

The hsCRP value in mg/L must be used. In order to calculate DAS28-hsCRP data must be present for all 4 components: TJC28, SJC28, patient's global assessment (VAS), and hsCRP. Component-level imputation will be performed for the calculation of DAS28-hsCRP for the imputed visits summaries. If at least 1 of the 4 components is nonmissing at the visit and the patient is still enrolled in the study, then use LOCF to fill in any missing values.

Based on the DAS-hsCRP, the following will be calculated:

- $\text{DAS28-hsCRP} \leq 3.2$
- $\text{DAS28-hsCRP} < 2.6$

Similarly,

$$\text{DAS28-ESR} = 0.56(\text{TJC28})^{1/2} + 0.28(\text{SJC28})^{1/2} + 0.70 \ln(\text{ESR}) + 0.014(\text{VAS}) \text{ [If ESR} = 0 \text{ in analysis data, set } \ln(\text{ESR}) = 0\text{]}$$

The ESR (Erythrocyte sedimentation rate) in mm/first hour must be used. In order to calculate DAS28-ESR data must be present for all 4 components: TJC28, SJC28, patient's global assessment (VAS), and ESR. Component-level imputation will be performed for the calculation

of DAS28-ESR for the imputed visits summaries. If at least 1 of the 4 components is nonmissing at the visit and the patient is still enrolled in the study, then use LOCF to fill in any missing values.

Based on the DAS-ESR, the following will be calculated:

- DAS28-ESR ≤ 3.2
- DAS28-ESR < 2.6

A NRI rule for the DAS28 binary endpoints will be applied for each visit as follows: if the DAS28 is missing at the visit or if the patient discontinued treatment or the study prior to the visit, then assign the patient as DAS28 non-responder.

Hybrid American College of Rheumatology Response Measure

The hybrid ACR (bounded) response measure will be obtained as described by the ACR Committee to Reevaluate Improvement Criteria (2007);

Table APP.1. Scoring Method for the Hybrid American College of Rheumatology Response Measure

ACR Status	Mean % Change in Core Set Measures ^a			
	<20	$\geq 20, <50$	$\geq 50, <70$	≥ 70
Not ACR20	Mean % change	19.99	19.99	19.99
ACR20 but not ACR50	20	Mean % change	49.99	49.99
ACR50 but not ACR70	50	50	Mean % change	69.99
ACR70	70	70	70	Mean % change

Abbreviations: ACR = American College of Rheumatology; ACR20 = 20% improvement in ACR criteria; ACR50 = 50% improvement in ACR criteria; ACR70 = 70% improvement in ACR criteria.

^a 1) Calculate the average percentage change in core set measures. For each core set measure, subtract score after treatment from baseline score and determine percentage improvement in each measure. Next, if a core set measure worsened by $>100\%$, limit that percentage change to 100% (set equal to -100% bound). Then, average the percentage changes for all core set measures. 2) Determine whether the patient has achieved ACR20, ACR50, or ACR70. 3) Using the table above, obtain the hybrid ACR response measure. To use the table, take the ACR20, ACR50, or ACR70 status of the patient (left column) and the mean percentage improvement in core set items; the hybrid ACR score is where they intersect in the table.

Simplified Disease Activity Index (SDAI)

